2.4.3 Interim Analyses and Data Monitoring

No interim analysis is planned in this study.

2.4.4 Multicenter Studies

Although this study is a multicenter study, treatment-by-center interaction will not be explored since the number of subjects for each center is not sufficient for such exploration.

2.4.5 Multiple Comparison/Multiplicity

The main focuses will be placed on the results of the primary analysis performed for the primary endpoint defined as change from baseline in the MADRS total score at Week 8 in the full analysis set. In the primary analyses, each Lu AA21004 group will be compared with the placebo group based on Holm's method to maintain the overall type I error rate below 5%. Other analytical results will be interpreted to support the results of the primary endpoint or to explore the characteristics of the efficacy of Lu AA21004. These results will be considered one measure suggesting the trends or characteristics of the efficacy. Thus, no adjustments for multiplicity will be performed.

2.4.6 Use of an “Efficacy Subset” of Subjects

In addition to analyses on the primary endpoint using the full analysis set, a secondary analysis will also be performed using the per protocol set to examine the robustness of the results from the perspective of sensitivity analysis.

2.4.7 Active-Control Studies Intended to Show Equivalence or Non-Inferiority

Not applicable in this study.

2.4.8 Examination of Subgroups

Analysis Set: Full Analysis Set

Analysis Variable: Change from baseline in the MADRS total score at Week 8 of double-blind

Variable(s): study drug (Week 8 - Baseline)

Stratum: Age (years) [Min<= - <=50, 51<= - <=Max]

Gender [Male, Female]

MADRS Total Score at [Min<= - <=30, 31<= - <=Max]

Baseline

Analytical Method(s): The following summaries will be provided for the above analysis variable(s) for each stratum.

- (1) The same mixed model for repeated measurements (MMRM) analysis of covariance as section “2.1.1 Primary Analysis” will be applied. Least Square (LS) means and the two-sided 95% confidence intervals at each visit will be provided for each treatment group. The point estimates of the differences in the LS means between each Lu AA21004 group and the placebo group (each Lu AA21004 – placebo group) and the two-sided 95% confidence intervals will be provided.

3 Safety Analysis

3.1 Treatment-Emergent Adverse Event

3.1.1 Overview of Treatment-Emergent Adverse Events

Analysis Set: Safety Analysis Set

Analysis TEAE

Variable(s):

Categories: Relationship to Study Drug [Related, Not Related]

Intensity [Mild, Moderate, Severe]

Analytical The following summaries will be provided for each treatment group and

Method(s): overall.

(1) Overview of TEAEs

- 1) All TEAEs (number of events, number and percentage of subjects)
- 2) Relationship of TEAEs to study drug (number of events, number and percentage of subjects)
- 3) Intensity of TEAEs (number of events, number and percentage of subjects)
- 4) TEAEs leading to study drug discontinuation (number of events, number and percentage of subjects)
- 5) Serious TEAEs (number of events, number and percentage of subjects)
- 6) Relationship of serious TEAEs to study drug (number of events, number and percentage of subjects)
- 7) Serious TEAEs leading to study drug discontinuation (number of events, number and percentage of subjects)
- 8) TEAEs resulting in death (number of events, number and percentage of subjects)

TEAEs will be counted according to the rules below.

[Number of subjects]

- Summaries for 2) and 6)

A subject with occurrences of TEAE in both categories (i.e., Related and Not Related) will be counted once in the Related category.

- Summary for 3)

A subject with multiple occurrences of TEAE will be counted once for the TEAE with the maximum intensity.

- Summaries other than 2), 3), and 6)

A subject with multiple occurrences of TEAE will be counted only once.

[Number of events]

For each summary, the total number of events will be calculated.

3.1.2 Displays of Treatment-Emergent Adverse Events

Analysis Set: Safety Analysis Set

Analysis TEAE

Variable(s):

Categories: Intensity [Mild, Moderate, Severe]
Time of Onset (day) [1<= - <=7, 8<= - <=14, 15<= - <=28,
29<= - <=42, 43<= - <=56, 57<= - <=Max]

Analytical Method(s): The following summaries will be provided for each treatment group and overall.

TEAEs will be coded using the MedDRA and will be summarized using SOC and PT. SOC will be sorted alphabetically, and PT will be sorted in decreasing frequency for tables provided by SOC and PT. SOC and PT will be sorted in decreasing frequency for tables provided by SOC only or PT only.

- (1) All TEAEs by SOC and PT
- (2) All TEAEs by SOC
- (3) All TEAEs by PT
- (4) Drug-Related TEAEs by SOC and PT
- (5) Intensity of All TEAEs by SOC and PT
- (6) Intensity of Drug-Related TEAEs by SOC and PT
- (7) TEAEs Leading to Study Drug Discontinuation by SOC and PT
- (8) Serious TEAEs by SOC and PT
- (9) All TEAEs by SOC and PT Over Time

The frequency distribution will be provided according to the rules below.

[Number of subjects]

- Summary tables other than (5), (6), and (9)

A subject with multiple occurrences of TEAE within a SOC will be counted only once in that SOC. A subject with multiple occurrences of TEAE within a PT will be counted only once in that PT. When calculating percentage of subjects with occurrence of TEAEs, the number of subjects in the safety analysis set will be used as the denominator.

- Summary tables for (5) and (6)

A subject with multiple occurrences of TEAE within a SOC or a PT will be counted only once for the TEAE with the maximum intensity. When calculating percentage of subjects with occurrence of TEAEs, the number of subjects in the safety analysis set will be used as the denominator.

- Summary table for (9)

A subject with a TEAE that occurs in more than one interval is counted in all the intervals that the TEAE occurs. For each time interval, a subject with multiple occurrences of TEAE within a SOC or a PT will be counted only once in that SOC or PT. When calculating percentages of subjects with occurrence of TEAEs for each time interval, the number of subjects at risk (i.e., subjects who either have an exposure or have an occurrence of TEAEs, during or after the corresponding time interval) will be used as the denominator. The number of subjects whose onset of the TEAEs is within the time interval will be used as the numerator.

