9.3.5 End of Double-blind Treatment Period or Early Termination

The examinations/observations/assessments listed below will be performed at 8 weeks after the start of double-blind treatment period (Day 56 ± 3; Visit 8) as evaluation at the end of double-blind treatment period. Subjects who prematurely discontinue the study during the placebo lead-in period or double-blind treatment period will be requested to visit the study site for early termination examinations/observations/assessments within 7 days after the day of study discontinuation wherever possible.

- Physical examination
- Weight
- Vital signs
- Concomitant medications
- Clinical laboratory tests (fasted)
- Pregnancy test (female subjects of childbearing potential only)
- Pharmacokinetic sampling (not performed at early termination)
- ECG procedure
- C-SSRS
- PTE/AE assessment
- MADRS
- HAM-D
- CGI-S

- CGI-I*
- SDS
- DSST
- PDQ-5
- QIDS-J
- Collection of the study medication dispensed at the last visit/Consultation about subjects' compliance

* The CGI-I score will be assessed comparing with that at Visit 3. However, at early termination prior to Visit 3, the CGI-I score will be assessed by comparing with that at Visit 2.

For all randomized subjects, the investigator must complete the End of Study eCRF page.

After evaluation at the end of double-blind treatment period or early termination, standard therapy may be performed as needed.

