9.3.6 Follow-up Period

A safety follow-up assessment will be conducted at 12 weeks after the start of double-blind treatment period (Day 84 ± 5). For subjects who prematurely discontinue the study during the placebo lead-in period or double-blind treatment period, the follow-up assessments will be made 28 ± 5 days after the last dose of the study medication. The follow-up assessments may either be conducted as a visit to the site or as a telephone contact. In the follow-up, the following will be assessed: outcomes of AEs continuing at Visit 8 or early termination visit, new SAEs developing during the follow-up period, and special interest AEs will be assessed. Female subjects of child-bearing potential will be asked to confirm whether they are pregnant or not.

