10.2 Procedures

10.2.1 Collection and Reporting of AEs

10.2.1.1 PTE and AE Collection Period

Collection of PTEs will commence from the time the subject signs the informed consent to participate in the study and continue until the subject is first administered study medication in the

placebo lead-in period. For subjects who discontinue prior to the first study medication administration in the placebo lead-in period, PTEs are collected until the subject discontinues study participation.

Collection of AEs will commence from the time that the subject is first administered study medication in the placebo lead-in period. Routine collection of AEs will continue until Visit 8 or Early Termination Visit.

Collection of SAEs or special interest AEs will continue until the end of the follow-up period.

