1.2 Demographics and Other Baseline Characteristics	13
1.2.1 Summary of Demographics and Other Baseline Characteristics	13
1.2.2 Medical History and Concurrent Medical Conditions	15
1.2.3 Medication History and Concomitant Medications	16
1.3 Treatment Compliance.....	16
1.3.1 Study Drug Exposure and Compliance.....	16
2 Efficacy Analysis.....	17
2.1 Primary Endpoint(s) and Analytical Methods.....	17
2.1.1 Primary Analysis.....	17
2.1.2 Secondary Analysis (1).....	18
2.1.3 Secondary Analysis (2).....	18
2.2 Secondary Endpoint(s) and Analytical Methods.....	19
2.3 Other Analysis/Additional Endpoint(s) and Analytical Methods	22
2.4 Statistical/Analytical Issues	31
2.4.1 Adjustments for Covariates.....	31
2.4.2 Handling of Dropouts or Missing Data.....	31
2.4.3 Interim Analyses and Data Monitoring.....	31
2.4.4 Multicenter Studies	31
2.4.5 Multiple Comparison/Multiplicity	31
2.4.6 Use of an “Efficacy Subset” of Subjects.....	32
2.4.7 Active-Control Studies Intended to Show Equivalence or Non-Inferiority	32
2.4.8 Examination of Subgroups.....	32
3 Safety Analysis	33
3.1 Treatment-Emergent Adverse Event.....	33
3.1.1 Overview of Treatment-Emergent Adverse Events	33

3.1.2 Displays of Treatment-Emergent Adverse Events.....	34
3.2 Pretreatment Events and Placebo Lead-in Adverse Events	35
3.2.1 Displays of Pretreatment Events.....	35
3.2.2 Displays of Placebo Lead-in Adverse Events	36
3.3 Laboratory and Other Safety Data	37
3.3.1 Laboratory Test Results	37
3.3.2 Vital Signs, Physical Findings and Other Observations Related to Safety.....	38
4 Significance Level and Confidence Coefficient	44
Amendment History (Version Management).....	45
[Appendix 1] Change Comparison Table for Lu AA21004/CCT-004	1
[Appendix 2]Definition of PCS Criteria	1

Glossary

- Treatment-emergent adverse event (TEAE): An adverse event which occurs on or after the start of double-blind study drug
- Placebo lead-in adverse event: An adverse event which occurs on or after the start of placebo lead-in study drug before the start of double-blind study drug
- Drug-related adverse event: An adverse event that is considered to be either probable, or possible related to the double-blind study drug will be treated as related.
- Descriptive statistics: number of subjects, mean, standard deviation, maximum, minimum, and quartiles
- PCS: Potentially Clinically Significant

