- Study Day: The day before the first dose of the double-blind study drug will be defined as Study Day -1 and the day of the first dose will be defined as Study Day 1.
- Follow-up Day: The day after the last dose of the double-blind study drug will be defined as Follow-up Day 1.
- Treatment Groups: Placebo, Lu AA21004 10 mg, Lu AA21004 20 mg
- MADRS total score: Sum of the 10 MADRS items
- HAM-D17 total score: Sum of the 17 HAM-D items
- HAM-D21 total score: Sum of the 21 HAM-D items
- SDS total score: Sum of the 3 SDS items
- MADRS response: Percentage of subjects whose MADRS total score decreased by a greater than or equal to 50% from baseline
- MADRS remission: Percentage of subjects whose MADRS total score decreased to 10 or less

Definition of TIME WINDOW

For each test/observation/evaluation item, all evaluable data (non-missing and acceptable according to the “Handling Rules for Analysis Data”) will be handled according to the following rules.

For each visit other than Week 8 (LOCF), observation in the corresponding time interval will be used. If more than one observation lies within the same visit window, the observation with the closest Study Day to the scheduled Study Day will be used. If there are two observations equidistant to the scheduled Study Day, the later observation will be used. The difference from the scheduled Study Day will be judged based on the Study Day and Follow-up Day.

For Week 8 (LOCF), the last observation obtained in the corresponding time interval will be used.

MADRS, CGI-S

Visit	Scheduled Study Day (days)	Time Interval (days)	
		Study Day	Follow-up Day
Screening	Study Day: -22	<= -12	-
Placebo lead-in	Study Day: -8	-11 - -5	-
Baseline (Week 0)	Study Day: -1	-4 - 1	-
Week 1	Study Day: 7	2 - 10	<8
Week 2	Study Day: 14	11 - 21	<8
Week 4	Study Day: 28	22 - 35	<8
Week 6	Study Day: 42	36 - 49	<8
Week 8	Study Day: 56	50 <=	<8
Week 8 (LOCF)	-	2 <=	<8

HAM-D

Visit	Scheduled Study Day (days)	Time Interval (days)	
		Study Day	Follow-up Day
Screening	Study Day: -22	<= -12	-
Placebo lead-in	Study Day: -8	-11 - -5	-
Baseline (Week 0)	Study Day: -1	-4 - 1	-
Week 8	Study Day: 56	2 <=	<8
Week 8 (LOCF)	-	2 <=	<8

CGI-I

Visit	Scheduled Study Day (days)	Time Interval (days)	
		Study Day	Follow-up Day
Baseline (Week 0)	Study Day: -1	<= 1	-
Week 1	Study Day: 7	2 - 10	<8
Week 2	Study Day: 14	11 - 21	<8
Week 4	Study Day: 28	22 - 35	<8
Week 6	Study Day: 42	36 - 49	<8
Week 8	Study Day: 56	50 <=	<8
Week 8 (LOCF)	-	2 <=	<8

SDS

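### In the last interval of the TEAE-over-time table, off-drug subjects enter the denominator only if they have an event, so lines driven by off-drug events read too high (minor)

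*SAP*

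**What the plan says.** Summary (9) in SAP 3.1.2 gives TEAEs by SOC and PT over time, and its last interval is open-ended from Day 57. The numerator is subjects whose TEAE begins in the interval. The denominator is "subjects who either have an exposure or have an occurrence of TEAEs, during or after the corresponding time interval".

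Four other provisions decide who that covers:

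- The SAP computes duration of exposure from first to last double-blind dose, with no allowance after the last dose.
- The SAP glossary defines a TEAE as "An adverse event which occurs on or after the start of double-blind study drug". It sets no end date.
- Protocol 10.2.1.1 separates two kinds of collection: "Routine collection of AEs will continue until Visit 8 or Early Termination Visit", whereas "Collection of SAEs or special interest AEs will continue until the end of the follow-up period".
- Protocol 9.3.5 places the end-of-treatment visit at "8 weeks after the start of double-blind treatment period (Day 56 ± 3; Visit 8"). Protocol 9.3.6 places the completers' safety contact at Day 84 ± 5. For early discontinuers, "the follow-up assessments will be made 28 ± 5 days after the last dose of the study medication".

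Protocol 13.1.5 makes the TEAE summaries descriptive, with no testing.

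**The concern.** An at-risk set should be fixed before one looks at who had the event. Here, once a subject is off drug, the only way into the denominator is to have a TEAE in that interval or later. Subjects who are off drug, still followed for SAEs and special interest AEs, and event-free are left out.

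This matters most from Day 57, because treatment is planned to end at about Day 56. A completer who takes the last dose on Day 56 has no exposure in the interval and appears only by having an event. The lines affected are SAEs and special interest AEs in follow-up, any AE between the last dose and Visit 8 or early termination, and the any-TEAE line. The purpose of the table is to show when events begin. A reader comparing intervals could take a rise in the last column for late onset when it comes from the shrunken denominator. Serious suicidality is among the events collected in follow-up, so some of these lines will be looked at closely.

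**Working it through.** The plan states no figure for this table, so there is nothing to reproduce. The check writes out the rule and applies it to assumed counts.

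**Rule.** For one arm in the interval from Day 57, let E = subjects dosed on Day 57 or later, A = off-drug subjects with any TEAE on or after Day 57, U = off-drug subjects still followed without a TEAE, and x = subjects on a line driven by off-drug events.

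- SAP percentage = x/(E + A)
- Percentage of those followed = x/(E + A + U)
- Ratio = (E + A + U)/(E + A), which exceeds 1 whenever U > 0

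**Inputs from the documents.** Planned arm size 160 (Protocol 13.3); Visit 8 on Days 53 to 59 (9.3.5); completers' contact on Days 79 to 89 (9.3.6); early discontinuers followed for up to 33 days after the last dose (9.3.6).

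**Assumed inputs.** 144 completers and 16 early stoppers in the arm; Visit 8 spread evenly over its seven days; dosing up to the visit; 1 to 3 off-drug subjects with any TEAE. Followed subjects number between 144 and 160, and 150 is used. The lower bound arises because a subject whose last dose is by Day 23 can leave follow-up by Day 23 + 33 = Day 56.

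**Number dosed on Day 57 or later.** Three of the seven visit days (57, 58, 59) qualify: E = 144 × 3/7 = 61.7, taken as 62.

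**One off-drug event on a line.**

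- SAP rule, A = 1: 1/(62 + 1) = 1/63 = 1.6%
- SAP rule, A = 3: 1/(62 + 3) = 1/65 = 1.5%
- Of those followed: 1/150 = 0.7%
- Ratio: 150/63 = 2.4 to 150/65 = 2.3

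**Lines driven by on-drug routine AEs** move slightly the other way, because the denominator gains follow-up SAE subjects who are no longer under routine collection. With 2 such events: 2/65 = 3.1% by the rule, against 2/62 = 3.2% of those dosed.

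**Share of collection time off drug.** For a completer, collection from Day 57 runs to Day 79 at the earliest (23 days) and Day 89 at the latest (33 days). With Visit 8 in its window and dosing stopped there, at most Days 57 to 59 (3 days) are on drug. The off-drug share is at least 20/23 = 87%.

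**Earlier intervals.** In Days 1 to 7 every treated subject has exposure, so there is no effect. For Days 29 to 42, assume 145 still dosed and one off-drug subject with an event. The ratio is then at most 160/146 = 1.1, even if all 160 are still followed.

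**The case against.** The best case against this is its reach. It concerns one column of one of nine TEAE displays, with no testing. Summaries (1) to (8) divide by the safety analysis set, and (8) is given over to serious TEAEs, so follow-up SAEs already appear elsewhere with an unselected denominator. That stands, and it makes the point minor.

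The size rests on assumed counts. That stands too: only the arm size and the visit windows come from the documents. A reader might infer a many-fold overstatement by supposing that very few subjects are dosed past Day 56. The documents give no such count and no basis for one. Nor is 87% a hard bound. The SAP leaves the Week 8 window open upward and provides an exposure category beyond Day 56, so later dosing is foreseen.

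The word occurrence could also be read to include ongoing events, since the SAP counts a TEAE in every interval in which it occurs. More off-drug subjects would then enter the denominator and the ratio would shrink, but entry would still depend on having an event. For hepatic impairment, scheduled laboratory tests end at Visit 8 or early termination and the follow-up contact may be a telephone call. The 150 followed are therefore too generous a comparator on that line.

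A simpler remedy would be one denominator of all subjects still followed, or a footnote. The first fails on routine AEs, whose collection stops at Visit 8: the 2 events above would show as 2/150 = 1.3% instead of 2/62 = 3.2%. A footnote leaves the misleading percentage in the table.

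**Conclusion.** The point holds as a minor one. Read literally, summary (9) admits off-drug subjects to its last denominator only through having a TEAE, and it overstates lines driven by off-drug events. Under the assumptions shown, a single such event reads about 1.5% to 1.6% instead of about 0.7%, which is one subject on the line. The size in this trial cannot be fixed, because the number dosed on Day 57 or later is not given.

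Two stronger readings are tempting and are not supported. One is that the comparison between arms is biased: the same rule applies to every arm, and nothing in the documents suggests that dosing past Day 56 differs by arm. The other is that the overall safety or efficacy conclusions are affected: the fault is confined to this descriptive table, mainly its last column.

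The SAP refers to separate Handling Rules for Analysis Data, which were not available. If they end TEAEs at some point after the last dose, the effect shrinks. Neither the protocol nor the SAP states such a limit.

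**What to change.** Define at risk in summary (9) without reference to events:

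- **On-treatment period:** from the first double-blind dose to the earlier of Follow-up Day 7 and Visit 8 or early termination. If there is no such visit, it ends on Follow-up Day 7.
- **Numerator:** subjects with a TEAE onset in the interval and within that period.
- **Denominator:** subjects whose period includes any day of the interval.
- **Separate display:** later SAEs and special interest AEs, over subjects still in follow-up.

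The SAP already has the pieces. It states that "The day after the last dose of the double-blind study drug will be defined as Follow-up Day 1", and its time windows for other data stop before Follow-up Day 8. Using that allowance, rather than cutting at the last dose, keeps events soon after dosing ends. The visit limit is needed because routine collection stops there.

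The cost is a short SAP edit, the visit date in the derivation, one extra display, and a footnote that summary (9) does not reconcile with summary (1). Summaries (1) to (8) keep every event as now defined.

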3.2 Pretreatment Events and Placebo Lead-in Adverse Events

3.2.1 Displays of Pretreatment Events

Analysis Set: All Subjects Who Signed the Informed Consent Form

Analysis PTE

Variable(s):

Analytical The following summaries will be provided for the above analysis variable(s).

Method(s): PTEs will be coded using the MedDRA and will be summarized using SOC and PT. SOC will be sorted alphabetically, and PT will be sorted in decreasing frequency.

- (1) All PTEs by SOC and PT
- (2) Serious PTEs by SOC and PT

The frequency distribution will be provided according to the rules below.

[Number of subjects]

A subject with multiple occurrences of PTE within a SOC will be counted only once in that SOC. A subject with multiple occurrences of PTE within a PT will be counted only once in that PT.

3.2.2 Displays of Placebo Lead-in Adverse Events

Analysis Set: All Subjects Who Received Placebo Lead-in Study Drug

Analysis Placebo lead-in adverse event

Variable(s):

Analytical The following summaries will be provided for the above analysis variable(s).

Method(s): Placebo lead-in adverse events will be coded using the MedDRA and will be summarized using SOC and PT. SOC will be sorted alphabetically, and PT will be sorted in decreasing frequency.

- (1) All Placebo Lead-in Adverse Events by SOC and PT
- (2) Serious Placebo Lead-in Adverse Events by SOC and PT

The frequency distribution will be provided according to the rules below.

[Number of subjects]

A subject with multiple occurrences of run-in AE within a SOC will be counted only once in that SOC. A subject with multiple occurrences of run-in AE within a PT will be counted only once in that PT.

